6.11.5 Exploratory Endpoints

Analysis of exploratory endpoints will be conducted on the FAS population.

The following exploratory endpoints will be analyzed:

QMD Ref: Worldwide-TMP-ST-005-7.0 Effective: 12Aug2019	Governing QMD: Worldwide-SOP-ST-001
Confidentiality Statement	
This document is the property of Worldwide Clinical Trials Inc. and may not be duplicated, copied, altered or removed from company without prior approval from Worldwide Quality Assurance or in compliance with Worldwide Standard Operating Procedures.	

Worldwide Clinical Trials Controlled Quality Management Document		
 WORLDWIDE CLINICAL TRIALS	Sponsor:	Synaptogenix, Inc.
	Protocol Number:	NTRP-101-204
STATISTICAL ANALYSIS PLAN. PHASE 2-3-4		

6.11.5.1 • Change from baseline in ADCS-ADL-Sev total score at Week 13 and Week 42

Analysis of this endpoint will be similar to analysis of primary efficacy endpoint. Analysis will be performed using the same MMRM model as described in Section 6.11.2.

6.11.5.2 • Change from baseline in MMSE-2 total score at Week 13 and Week 42

Analysis of this endpoint will be similar as described in Section 6.11.7.1 but for post-baseline changes in MMSE-2 total score.

6.11.5.3 • Change from baseline in NPI total score at Week 13 and Week 42

Analysis of this endpoint will be similar as described in Section 6.11.7.1 but for post-baseline changes in MMSE-2 total score.

6.12 Safety Analyses

The safety analyses will be presented by the treatment received for the Safety Analysis Set.

6.12.1 Adverse Events

Adverse events will be coded using Medical Dictionary of Regulated Activities (MedDRA, version 23.0 or later) primary system organ class (SOC) and preferred term (PT).

Treatment Emergent AEs (TEAEs) are defined as events with an onset on or after the first randomized treatment.

Severity grade will be defined by variable “Severity/Intensity” of the CRF. Maximum severity will be assumed for an AE with missing severity.

Relationship to study drug will be defined by variable “Causality” of the CRF. Maximum relationship will be assumed for an AE with missing causality.

An AE will be considered as resulting in discontinuation of study treatment if variable “Action taken with Study Treatment” equals to “DRUG WITHDRAWN”.

An AE will be considered as lead to study discontinuation if the subject didn’t complete the study with primary reason for termination equals to “ADVERSE EVENT” and the AE has number equals to value of variable “Adverse Event Number” on page “End Of Study” of the CRF.

QMD Ref: Worldwide-TMP-ST-005-7.0 Effective: 12Aug2019	Governing QMD: Worldwide-SOP-ST-001
Confidentiality Statement	
This document is the property of Worldwide Clinical Trials Inc. and may not be duplicated, copied, altered or removed from company without prior approval from Worldwide Quality Assurance or in compliance with Worldwide Standard Operating Procedures.	

Worldwide Clinical Trials Controlled Quality Management Document		
 WORLDWIDE CLINICAL TRIALS	Sponsor:	Synaptogenix, Inc.
	Protocol Number:	NTRP-101-204
STATISTICAL ANALYSIS PLAN. PHASE 2-3-4		

An AE will be considered as AE of Special Interest (AESI) if variable “Was this event considered Adverse Event of Special Interest (AESI)?” equals to “YES”.

The following tables will be presented, by SOC and PT, both sorted alphabetically, with summaries for each treatment group and overall:

- Overview of AEs
- TEAEs
- TEAEs by maximal severity grade
- TEAEs by maximal relationship to study treatment
- Serious TEAEs (TESAEs)
- TEAEs resulting in discontinuation of study treatment
- TEAEs resulting in discontinuation of study treatment by maximal relationship to study treatment
- TEAEs that lead to study discontinuation by maximal relationship to study treatment
- TESAEs by maximal relationship to study treatment
- Treatment Emergent Adverse Events of Special Interest (TEAESI)

Following listings on AEs will be provided:

- Pre-treatment AEs
- TEAEs
- Serious TEAEs
- TEAEs resulting in discontinuation of study treatment
- TEAE with fatal outcome

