6.1.22 Early Treatment Discontinuation and Follow-up

If for any reason, the investigator, subject or caregiver decide to discontinue the study drug or withdraw consent from the study, the subject and caregiver should be encouraged to complete an early termination (ET) visit and follow-up visit(s) as below:

- ET visit:
 - If the subject is withdrawn from the study at or before Week 13, subject will not enter Treatment Period 2.
 - If possible, schedule ET visits for 30 days (+/-2 days) after the last study drug dose administration
 - The ET reason must be documented with as much detail as possible in the EDC and in the source documents.

CONFIDENTIAL

- Follow-up Visits: Despite discontinuation of the study drug dosing, subjects and caregivers should be encouraged to return for additional follow-up visits for the duration of the trial, in order to monitor for safety and any changes in cognition.
 - The follow-up visits should be scheduled to coincide with the cognitive assessment visits scheduled after the study drug discontinuation (i.e., weeks 5, 9, 13, 15, 20, 24, 28, 30).
 - The below assessments should be completed at all follow-up visits:
 - SIB
 - Vitals
 - Adverse Events
 - Concomitant medications
 - If the subject is willing to return for only one follow-up visit, please schedule this visit to occur approximately 30 days (+/-2 days) following the last study drug dosing.

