7 ADVERSE EVENTS AND OTHER SAFETY EVALUATIONS

7.0 Definition of Adverse Events

An AE is any untoward medical occurrence associated with the use of a drug in humans, whether or not considered drug related. An AE (also referred to as an adverse experience) can be any unfavorable and unintended sign (e.g., clinically significant abnormal laboratory finding), symptom, or disease temporally associated with the use of a drug, without any judgment about causality.

The PI is responsible for obtaining information about all medical emergencies during the clinical study. The PI's contact information will be located in the body of the informed consent form (ICF) and subjects/caregivers will be encouraged to contact the PI or clinical site personnel during any clinical study-related emergency.

All adverse events spontaneously reported by the subject and/or caregiver in response to an open question or revealed by observation will be recorded during the study regardless of relationship to the study drug. All AEs will be monitored and recorded for the progress of the event until it resolves or reaches a clinically stable outcome. Adverse events that are not resolved at the time of database lock will be recorded as ongoing.

The AE and SAE reporting period starts from the time of consent to the last study visit.

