7.6 Reporting Adverse Events

The PI should instruct all subjects/caregivers on the procedure for reporting AEs/SAEs to the appropriate clinical site personnel. For each AE reported by parents/guardians, clinical site personnel should obtain all required information to complete the eCRF.

The PI or designee should document all AEs/SAEs in subjects' source documentation and on the AE eCRF.

In addition to standardized reporting procedures, worsening or exacerbation of concurrent conditions in subjects will also be reported as AEs, and will follow the designated reporting format.

The following should be recorded with each SAE/AE:

- The nature of the AE, with a diagnosis wherever possible
- Date of event
- Assessment of intensity
- Is this an SAE?
- Relationship to study drug or trial-related procedures
- Action taken regarding study drug treatment
- Outcome

If the intensity of an already reported AE increases, then a new AE eCRF must be completed for that AE. The date of change would be included as the end date for the originally reported AE, and the start date for the new AE of greater intensity.

The clinical research associate is responsible for source document verification of all safety events.

If the clinical site becomes aware of an SAE, regardless of causality, within 30 days following the last administration of investigational product, the SAE should be recorded and reported immediately to the Sponsor. An SAE that occurs more than 30 days after the last dose will NOT be collected unless the PI considers that the event is related to the investigational product.

The sponsor should be informed if the PI becomes aware of any unusual safety information or any potential drug-related safety information, even after a subject completes the study

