7.6.1 SAE reports

All SAEs, whether or not considered associated with study treatment or study-related procedures, must be reported on the eCRF immediately and no later than 24 hours after the site becomes aware of the event. Follow-up information must be provided promptly as requested.

CONFIDENTIAL

The PI is obligated to provide as much information about the event as possible on the eCRF provided and as requested by the Sponsor or Medical Monitor.

In general, this will include a description of the SAE in sufficient detail to allow for a complete medical assessment of the case. The pharmacovigilance physician or designee will review the SAE including the SAE criteria, the relationship to study medication, the expected or unexpected assessment, and inform the Sponsor by phone and e-mail immediately.

The following AEs should also be reported to the Sponsor's designated Medical Monitor immediately:

- severe injection/infusion site reactions (ulceration or necrosis that is severe; operative intervention indicated)
- systemic hypersensitivity reactions
- myalgia

All additional follow-up evaluations must be reported by the site to the medical monitor, or designee, immediately after notification of the additional information.

An SAE will be followed until it resolves or reaches a clinically stable outcome. AEs/SAEs that have not resolved by study closure will be considered ongoing.

An SAE that occurs after the 30-day safety visit will NOT be collected unless the PI determines that the event is related to the investigational drug product.

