9.8.1 Adverse Events

Adverse events will be coded using the most recent version of Medical Dictionary for Regulatory Activities (MedDRA). Treatment Emergent AE's (TEAE) are defined as events with an onset on or after the first randomized treatment. TEAEs will be summarized by treatment group, System Organ Class, and preferred term. The following TEAE summaries will be provided:

- Overall (*i.e.*, regardless of severity or relationship to treatment)
- By severity grade (mild, moderate, severe, life threatening or death for SAEs)
- By relationship to clinical trial treatment (definitely related, probably related, possibly related, unlikely related, unrelated)

Unless otherwise specified, at each level of subject summarization, a subject will be counted only once. If there is more than one occurrence of an event, the event of the worst severity or the worst-case relationship category will be summarized.

In addition, separate summaries of serious adverse events, and adverse events resulting in discontinuation of study treatment will be presented.

AEs leading to premature discontinuation of clinical trial treatment, AEs that lead to study discontinuation, AEs that lead to death and Serious Adverse Events (SAEs) will also be summarized by treatment group and relationship.

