16.5 Protocol Version 6.0 September 1, 2022

The protocol previously included a follow-up visit at Week 42. The Week 42 visit has been removed. However, data collected at this visit for subjects who completed the visit prior to implementation of this amendment will be included in the analyses as described.

References to PKC ϵ testing and analysis have been removed, since no PKC ϵ samples were collected for this trial.

CONFIDENTIAL

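### The treatment-emergent window has no end, so AE percentages mix about 294 and 210 days of follow-up and can attenuate an on-drug difference

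*SAP*

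**What the plan says.** SAP 6.12.1: "Treatment Emergent AEs (TEAEs) are defined as events with an onset on or after the first randomized treatment". Protocol 9.8.1 agrees: TEAEs "are defined as events with an onset on or after the first randomized treatment". Neither sets a last day.

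How long events are collected is set elsewhere:

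- Protocol 7.0: "The AE and SAE reporting period starts from the time of consent to the last study visit".
- Protocol 16.5: "The protocol previously included a follow-up visit at Week 42. The Week 42 visit has been removed". The same entry keeps Week 42 data from subjects who had already completed that visit. SAP 6.12.2, 6.12.5 and 6.12.6 still list Week 42 for laboratory tests, physical examination and C-SSRS.
- Protocol 6.1.21 includes adverse events among the procedures at follow-up visits.
- Protocol 6.1.22, on subjects who stop study drug: "subjects and caregivers should be encouraged to return for additional follow-up visits for the duration of the trial". AEs are recorded at each of these visits.
- For serious events, Protocol 7.6 says: "An SAE that occurs more than 30 days after the last dose will NOT be collected unless the PI considers" the event related to the product. Protocol 7.6.1 says: "An SAE that occurs after the 30-day safety visit will NOT be collected unless the PI determines" that it is related.

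The AE tables in SAP 6.12.1 and SAP 11 (14.3.1.1 to 14.3.1.10) have no on-treatment window, no exposure-adjusted rate and no split by time. The protocol synopsis, under Statistical Considerations, promises safety summaries by treatment group and by time in study. SAP 9 does not list the loss of that summary as a change.

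**The concern.** A percentage of subjects with an event means little unless the period at risk is known and similar across subjects. Here the period depends on whether a subject had the Week 42 visit before it was dropped and, for subjects who stopped drug, on whether they kept attending. Time well after the last infusion adds events to both arms. If those late events are mostly background, they bring the arms closer together in a subject-level percentage.

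Safety and tolerability are part of the primary objective (Protocol 3.0). Protocol 9.3 rules out formal testing of safety data, so these descriptive tables are the whole AE comparison. No model downstream corrects for unequal follow-up.

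Serious events raise a second issue. After about 30 days off drug, Protocol 7.6 and 7.6.1 collect only those considered related, while Protocol 7.0 has no such limit. Late events in the serious-event tables, in particular serious events by relationship (14.3.1.9), could then be a selected set.

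**Working it through.** The plan states no AE incidence, so there is no figure of its own to reproduce.

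**Step 1: windows.** Dose 14 is on Day 182 (Protocol 6.1.17) and Week 30 is Day 210 (Protocol 6.1.19). Week 42 is 42 × 7 = Day 294.

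- Under version 6.0, follow-up ends 210 − 182 = 28 days after dose 14.
- With Week 42, it ends 294 − 182 = 112 days after dose 14. That is 84 more off-drug days and a window 294/210 = 1.4 times as long.
- As an example of a discontinuer, take a last infusion at Week 5 (Day 35) and attendance to Day 210. This subject has 210 − 35 = 175 days after the last infusion, all inside the TEAE window.

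AE collection at Week 42 is an inference from Protocol 6.1.21, 7.0 and 16.5. The current Schedule of Activities has no Week 42 column.

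**Step 2: model.** Assume a constant placebo hazard λ per day. The bryostatin hazard is HR × λ to Day 210 and λ afterwards. A share f of each arm is followed to Day 294; the documents do not give f, so it runs from 0 to 1.

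- Placebo incidence: 1 − exp(−210λ) at Week 30, and 1 − exp(−294λ) at Week 42.
- Bryostatin incidence: 1 − exp(−210 × HR × λ) at Week 30, and 1 − exp(−210 × HR × λ − 84λ) at Week 42.
- Among subjects followed to Week 42, the risk difference is therefore the Week 30 value times exp(−84λ).

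**Step 3: any TEAE.** Study 203 placebo was 24/55 = 43.6% (Protocol 2.1.1.3), taken as 105 days (assumption). λ = −ln(1 − 24/55)/105 = 0.00546. With HR 1.5:

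- Week 30: placebo 68.2%, bryostatin 82.1%, difference 13.9 points.
- Week 42: placebo 79.9%, bryostatin 88.7%, difference 8.8 points. The factor is exp(−84 × 0.00546) = 0.632.
- Half followed to Week 42: 74.1% and 85.4%, difference 11.3 points.

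**Step 4: how the result depends on event frequency.** The second row uses the study 202 placebo rate for treatment-related TEAEs (8 subjects, 16.7%, Protocol 2.1.2.3), and the third an assumed 5%. Both are taken over 105 days.

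| Event type, HR to Week 30 | Factor exp(−84λ) | Risk difference, f = 0 / 0.5 / 1 (points) | Risk ratio, f = 0 / 0.5 / 1 |
|---|---|---|---|
| Any TEAE, 43.6%, HR 1.5 | 0.632 | 13.9 / 11.3 / 8.8 | 1.20 / 1.15 / 1.11 |
| Treatment-related, 16.7%, HR 2 | 0.864 | 21.2 / 19.8 / 18.3 | 1.69 / 1.56 / 1.46 |
| Single term, 5%, HR 2 | 0.960 | 8.8 / 8.6 / 8.4 | 1.90 / 1.75 / 1.63 |

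With HR 1 the arms are equal at every f. For uncommon terms the risk difference barely moves, and the effect shows mainly in the risk ratio.

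**Step 5: serious events.** Set side by side, Protocol 7.0 runs SAE reporting to the last study visit, 7.6 limits it to 30 days after the last dose unless related, and 7.6.1 limits it to the 30-day safety visit unless related. For a subject seen at Week 42, or a discontinuer still attending, these rules give different answers about the same unrelated SAE. The documents do not show which one sites followed.

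**The case against.** **The effect may be absent.** In study 203, TEAE incidence was 43.4% on bryostatin and 43.6% on placebo, a hazard ratio of ln(1 − 23/53)/ln(1 − 24/55) = 0.99. A reader might take the fall from 13.9 to 8.8 points (37%) as the expected loss. The documents do not support that: it needs an assumed HR of 1.5, equal off-drug hazards and every subject reaching Week 42. It stands only as the far end of a range. A true difference is not ruled out for all event types, though. In study 202, treatment-related TEAEs occurred in 17 subjects (37.0%) on 20 µg and 8 (16.7%) on placebo.

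**Era cannot bias the comparison.** This stands. Allocation is 1:1, so the share reaching Week 42 is balanced in expectation. A reader might also infer that incidence climbs as the protocol advances. It would go the other way, being lower under version 6.0. Randomization does not, however, balance who discontinues or who then keeps attending.

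**Late events may be drug effects.** The longest mean half-life reported in study 202 is 5.37 h (Protocol 2.1.2.5), which tempts one to call all late events background. The protocol's rationale is lasting synaptic change, and Protocol 3.0 asks how long effects persist, so half-life alone does not settle it. This is a reason to keep late events visible by arm; it does not justify pooling them unmarked.

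**A cap has its own fault.** Ending the window 30 days after the last infusion makes observation time depend on discontinuation. If one arm stops more often, the cap removes time and events from it. This also stands, and the fix has to answer it. Nor would a cap make incidence comparable with the 15-week studies: the model gives 68.2% at Week 30 against 43.6%.

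**Not every table is affected alike.** For subjects who completed dosing, an event after Week 30 cannot lead to withdrawal of study drug, so Tables 14.3.1.6 and 14.3.1.7 hardly change. Unrelated late SAEs may not be collected at all.

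**Conclusion.** The definition is open-ended in both documents, and the AE tables as planned pool subjects with unequal off-drug follow-up: about 294 against 210 days by Week 42 attendance, plus a variable tail for discontinuers. This raises incidence in subjects followed to Week 42 and can attenuate an on-drug difference. It does not tilt the comparison through era.

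The size is uncertain. Under the stated assumptions the loss in risk difference runs from nothing (HR 1, or nobody at Week 42) to 5.1 points for any TEAE (13.9 − 8.8), and is 0.4 points at most for the 5% term (8.8 − 8.4). These are illustrations; the share reaching Week 42 and the true hazards are not in the documents.

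The conflict between Protocol 7.0 and Protocol 7.6 and 7.6.1 is separate and needs no model. As written, late serious events may be collected selectively by judged relationship. The change is worth making before unblinding because it is cheap and safety is part of the primary objective. It affects description only; no test or power figure depends on it.

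**What to change.** In SAP 6.12.1, before unblinding:

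1. Make the main TEAE tables cover onset or worsening from the first infusion to 30 days after the subject's last infusion, in line with the 30-day SAE period in Protocol 7.6. On schedule, a version 6.0 completer loses nothing (182 + 30 = Day 212, after the Day 210 visit). With ±2-day visit windows, dose 14 on Day 180 and a visit on Day 212 could move two days of events.
2. Put later events in a separate post-treatment table and listing by arm, with the number of subjects still under observation.
3. Keep an overview of all events after the first dose, with time at risk by arm, so that no event is lost and any effect of informative discontinuation can be seen.
4. Add the by-time-in-study AE summary promised in the synopsis, with numbers at risk, or an exposure-adjusted equivalent.
5. Have the sponsor reconcile Protocol 7.0, 7.6 and 7.6.1 on SAE collection, and state in the report which rule was in force for late serious events.

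The cost is one definition and a few extra tables. Late events leave the main table but stay visible by arm.

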
Statistical Considerations:
 
The primary objective for efficacy is to evaluate whether bryostatin is better than the control with respect to the primary and secondary SIB endpoints. Efficacy analyses will be conducted for the full analysis set (FAS), consistent with the modified intention-to-treat principle, defined as all randomized subjects who received at least one dose of randomized study medication and who had at least one post-baseline efficacy assessment.
 
The per protocol analysis set (PP) is defined as all patients completing the study without major protocol deviations. To be included, subjects must have received at least 11 of the 14 doses (80%). The completer analysis set (CAS) will be defined as all randomized subjects who completed two 12-week courses of treatment, and who have a Week 28 SIB assessment. Efficacy analyses will also be conducted for the PP and CAS sets.
 
Adverse event and other safety data will be analyzed descriptively in all subjects who received any dose of study drug (including partial infusions). These data will be summarized by treatment group and by time in study.
		

Eligibility Criteria:**Inclusion**

1. Written informed consent from caregiver and subject (if possible) or legally acceptable representative if different from caregiver
2. Male and female subjects 55-85 years of age inclusive
3. Cognitive deficit present for at least 2 years that meet the diagnostic criteria for probable Alzheimer's dementia.¹ The diagnosis must be confirmed at the time of the screening visit
4. MMSE-2 score of 10-18 inclusive (applies to Screening Visit only)
5. Patients must have a baseline SIB total score of at least 60 and may not have a SIB score >93 at screening
6. Neuroimaging computerized tomography (CT) or Magnetic Resonance Imaging (MRI) within the last 24 months consistent with a diagnosis of probable AD without any other clinically significant co-morbid pathologies. If there has been a significant change in the subject's clinical status since the last imaging study that is not consistent with progression of the subject's AD, an imaging study should be performed to confirm eligibility
7. Reliable caregiver(s) or informant(s) who attends the subject at least an average of 3 hours or more per day for 3 or more days per week and who will agree to accompany the subject to the clinic visits and reliably complete the caregiver questions
8. Adequate vision and motor function to comply with testing

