4 INVESTIGATIONAL PLAN

4.0 Overview of Study Design

This is a randomized double-blind placebo-controlled exploratory study assessing bryostatin for the treatment of moderately severe Alzheimer's disease in subjects not receiving memantine treatment. The first treatment period of the study is 15 weeks in duration, including safety and efficacy evaluation 30 days after the last treatment. Eligible subjects will be stratified based on SIB total scores at baseline and will be randomized 1:1 to treatment with 20 μ g bryostatin or placebo for two 12-week courses of treatment. The balance by treatment arms of baseline SIB total scores will be monitored in real time. Study drug is administered IV by continuous infusion. The first two doses of study drug will be a loading dose 20% higher (i.e., 24 μ g) than the assigned dose and will be administered one week apart. Thereafter, the assigned dose of 20 μ g will commence with the third dose and be administered every other week for 5 doses. The second treatment period, beginning at Week 15, will be identical to the first. Subjects are scheduled to receive seven doses over 12 weeks during the first treatment period and seven doses over 12 weeks in the second period according to the original blinded, randomized treatment assignment. Safety and efficacy assessments will be

CONFIDENTIAL

done as indicated on the Schedule of Activities (Table 1). The primary endpoint is the total SIB score assessment obtained at Week 28, after completion of two courses of treatment.

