7.1 Adverse Event of Special Interest - Myalgia

Myalgia has been reported as the dose limiting toxicity across the oncology studies. The incidence of myalgia appears to be dose dependent and cumulative. However, it has been reported in subjects receiving doses as low as 5µg/m². The myalgia has been investigated in some studies but not all. No increase in muscle enzymes were found in the cases investigated. EMG was abnormal in one subject who received 65µg/m² and suggested a patchy myositis. An MRI done in another subject was normal.

CONFIDENTIAL

For all cases of myalgia despite the severity, a narrative will be created documenting onset, severity, treatment and outcome. Muscle enzymes, CPK, will be collected for all cases and compared to baseline values. Additional investigations are at the discretion of the investigator.

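### The SAP's adverse-event tables drop the synopsis's time-in-study split without declaring it, so they cannot show incidence by treatment course

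*SAP*

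**What the plan says.** The synopsis (Statistical Considerations) covers adverse-event and other safety data in all dosed subjects and says: "These data will be summarized by treatment group and by time in study". The body of the protocol does not repeat the time element. Protocol 9.8.1 says "TEAEs will be summarized by treatment group, System Organ Class, and preferred term", and Protocol 9.3 also works by treatment only. Protocol 9.8.1 adds a counting rule: "Unless otherwise specified, at each level of subject summarization, a subject will be counted only once". Repeat occurrences are reduced to the worst severity or relationship.

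SAP 6.12.1 says: "The following tables will be presented, by SOC and PT, both sorted alphabetically, with summaries for each treatment group and overall". Ten tables follow, matching 14.3.1.1 to 14.3.1.10 in SAP section 11. The same section defines the window: "Treatment Emergent AEs (TEAEs) are defined as events with an onset on or after the first randomized treatment".

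On the design, Protocol 4.0 says: "The second treatment period, beginning at Week 15, will be identical to the first". Each subject is therefore scheduled for 7 + 7 = 14 infusions in the same arm.

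SAP section 6 gives itself precedence over the protocol's analysis plans. SAP section 9 lists three changes: false-discovery-rate control is dropped, the visit list of one secondary endpoint is altered, and GEE is replaced by MMRM. The time split for adverse events is not among them.

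**The concern.** The Alzheimer's studies summarised in Protocol section 2.1 gave either a single dose or one seven-dose course. What this trial adds on safety is the second course, and safety and tolerability are part of the primary objective (Protocol 3.0). A change in event rates between courses is what a reader of the report will look for. The planned adverse-event tables give one figure per term and arm for the whole study, so that change would not be visible in them.

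Protocol 7.1 adds a reason to look, in its account of the oncology experience: "The incidence of myalgia appears to be dose dependent and cumulative". Both safety board reviews are triggered by counts of subjects who have had about four doses, which falls within the first course, and the adverse-event tables for those reviews (SAP section 8) have no time split either. The final tables are therefore the main planned place to see second-course rates by arm. As written, the synopsis commitment lapses without anyone having recorded a decision to drop it.

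**Working it through.** The documents give no figure on this point to reproduce. The check is a comparison of texts, followed by illustrations.

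**1. Texts side by side**

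| Source | Split for adverse events | Time element |
|---|---|---|
| Protocol synopsis | treatment group and time in study | yes |
| Protocol 9.3, 9.8.1 | treatment, SOC, preferred term | none |
| SAP 6.12.1; tables 14.3.1.1–14.3.1.10 | treatment, SOC, preferred term | none |
| SAP 8 (safety board tables) | summaries of TEAEs, serious TEAEs and special-interest events, some by relationship | none |
| SAP 9 (declared changes) | not mentioned | – |

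By contrast, exposure (SAP 6.9), laboratory data and vital signs (SAP 6.12.2, 6.12.3) and weight (table 14.3.6.2) are tabulated by visit. Adverse events are the exception.

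**2. What a pooled, once-counted incidence leaves open**

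Let p1 and p2 be the course-1 and course-2 incidences. If the courses are independent and every subject enters both, the pooled incidence is P = 1 − (1 − p1)(1 − p2).

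- 25% then 16%: 1 − 0.75 × 0.84 = 37%
- 16% then 25%: 1 − 0.84 × 0.75 = 37%
- 20.6% in each: 1 − 0.794 × 0.794 = 37.0%
- 37% then 0%, or 0% then 37%: 37%
- 37% in each, always in the same subjects (independence dropped): 37%

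A fall, no change and a rise all give the same table entry. The 37% only sets a scale: it is the share of the 20 µg arm with a treatment-related event over one course in study 202 (Protocol 2.1.2.3).

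**3. Denominator**

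In study 203, 48 + 48 = 96 subjects completed, out of a Safety Analysis Set of 108 (Protocol 2.1.1.2): 96/108 = 88.9%. Assume the same share enters course 2 here. A true 10% among entrants then appears as 0.889 × 10% = 8.9% of all dosed. The loss is 1.1 points, or 0.011 × 50 ≈ 0.6 of a subject in an arm of 50. This part of the problem is small.

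**4. How far pooling hides a doubling**

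Suppose course-1 incidence is known to be 5%. Whatever the overlap between courses, P lies between max(p1, 0.889 p2) and p1 + 0.889 p2.

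- Unchanged (p2 = 5%): 0.889 × 5% = 4.4%, so P is 5% to 9.4%.
- Doubled (p2 = 10%): 0.889 × 10% = 8.9%, so P is 8.9% to 13.9%.

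These ranges overlap only from 8.9% to 9.4%. The ambiguity in step 2 arises because the tables do not show the course-1 rate.

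**5. Windows**

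Dose 8 is at Week 15. Course 1 spans 15 weeks. Course 2 spans 30 − 15 = 15 weeks to Week 30, but 42 − 15 = 27 weeks for subjects who completed Week 42 before that visit was removed.

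**6. Onset dates**

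Under SAP 6.2.5, an event with no start date that is ongoing, or that ended on or after first dose, is given the date of first dose and so falls in course 1. A year-only start in the year of first dosing gets the same date, since 1 January cannot be later. A start known only to the month moves to the first of that month (or to first dose, if that was in the same month), which can carry it back across dose 8.

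**7. Precision of a split**

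Assume about 0.873 × 50 ≈ 44 per arm in course 2, using the 48/55 bryostatin completion in study 203. For 37.0% versus 16.7% (the study 202 rates at 20 µg and placebo), the half-width is 1.96 × √[(0.37 × 0.63 + 0.167 × 0.833)/n]: 17 points at n = 50 and 18 at n = 44. With no events, the one-sided 95% upper bound 1 − 0.05^(1/n) is 5.8% at n = 50, 6.6% at n = 44 and 7.2% at n = 40. A split is descriptive.

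**The case against.** The best defence is that the SAP follows the body of the protocol. The time element is in one synopsis sentence, is not defined as treatment course, and is absent from Protocol 9.3 and 9.8.1. The explicit second-course question in Protocol 3.0 is about effectiveness, and neither document promises a comparison of tolerability between courses. The other safety data are largely tabulated by visit. Listings of TEAEs, serious TEAEs and discontinuations are planned, every myalgia case gets a narrative that includes onset (Protocol 7.1), and SAP section 6 allows extra tables in the study report.

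Most of this stands, and it confines the point to the adverse-event tables. It does not remove it. Listings and narratives give no rates per course by arm, and tables chosen after unmasking are not prespecified. An inconsistency within the protocol still has to be resolved one way or the other.

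Two further objections are fair. The once-per-subject rule is in Protocol 9.8.1, with an exception clause, and not in SAP 6.12.1. The SAP's maximal-severity and maximal-relationship tables work that way, but without the table shells one cannot tell whether event counts will also appear. And the description of myalgia as cumulative comes from oncology. Protocol 4.1 says the pattern was not seen in studies 201 and 202, where 4 of the 5 cases in study 202 were at 40 µg. Those studies gave one dose and one course, so they do not settle what fourteen doses do, but the documents do not show a cumulative effect in this population.

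**Conclusion.** The point holds for the planned tables. A commitment to summarise adverse events over time is made in the synopsis, met by none of the ten SAP tables, and not declared as dropped. Those tables cannot show incidence per course by arm. In the illustration a pooled 37% is compatible with anything from 37%/0% to 0%/37%, assuming independent courses with every subject in both. Dilution of the denominator is a minor part, about one percentage point on a 10% rate if course-2 entry resembles study 203 completion.

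A reader might infer that the trial could never say how well the second course was tolerated. The documents do not support that: event dates are recorded (Protocol 7.6), and listings and narratives are planned. Nor do they support the inference that a pooled figure looks the same whether or not risk doubled. With a known 5% in course 1 the two cases mostly separate (5% to 9.4% against 8.9% to 13.9%). What is missing is the course-1 rate itself. This should be corrected before unmasking. It does not affect the efficacy analysis or the sample size.

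**What to change.** Add to SAP 6.12.1 and section 11 descriptive tables of TEAEs, serious TEAEs, events of special interest and events leading to discontinuation, by course of onset and arm:

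- **Split** at the dose 8 infusion (Week 15). Count a subject once per course, with subjects dosed in that course as the denominator.
- **Windows:** end course 2 at Week 30 and show later events separately, or give exposure-adjusted rates. For subjects who never receive dose 8 but stay in follow-up, close the course-1 window at the Week 15 date and show later events separately.
- **Onset dates:** state how events with missing or partial start dates are assigned to a course, and report how many were assigned by imputation.
- **Reading:** compare bryostatin with placebo within the same course. Those who enter course 2 are selected for having stayed on treatment, so a course-2 versus course-1 contrast within one arm is not a clean comparison.

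Between-arm confidence intervals for chosen terms are optional. Align Protocol 9.8.1 with the synopsis. If the sponsor prefers not to split, list the omission with its reason in SAP section 9 and amend the synopsis.

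The cost is a few extra tables from dates already collected, with small counts and wide intervals. No extra subjects or visits are needed.
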